## PROTOCOL SYNOPSIS – BMT CTN 0702 LONG-TERM FOLLOW-UP PROTOCOL

### Continued, Long-Term Follow-Up and Lenalidomide Maintenance Therapy for Patients Who Have Enrolled on BMT CTN 0702

- Co-Principal Investigators:** [name], [name], and [name]
- Study Design:** The study is designed to provide continued, long-term follow-up on patients enrolled on BMT CTN 0702 who have not experienced progression, as well as to offer optional long-term lenalidomide maintenance therapy to those BMT CTN 0702 patients who have completed 3 years of protocol-defined maintenance therapy without evidence of disease progression.
- Primary Objective:** The primary objective is to compare progression-free survival (PFS) as a time to event analysis between the three randomized treatment arms from the BMT CTN 0702 protocol as a pairwise comparison. The analysis will be conducted once all surviving patients have been followed for at least 5-years post randomization on the BMT CTN 0702 protocol.
- Secondary Objectives:** Secondary objectives include the cumulative incidence of second primary malignancies (SPM), probability of overall survival (OS), probability of event-free survival (EFS) and Health Quality of Life (QOL) on all patients, including those not receiving long-term lenalidomide maintenance therapy.
- Eligibility Criteria:** Patients eligible for long-term follow-up are those who were enrolled and randomized on the BMT CTN 0702 protocol and who are alive at the end of the BMT CTN 0702 protocol-defined follow-up period without progression. Patients eligible for long-term lenalidomide maintenance therapy include patients who have completed 3 years of BMT CTN 0702 protocol-defined lenalidomide maintenance therapy with no evidence of disease progression.
- Treatment/Follow-Up:** All patients who consent to the long-term follow-up protocol will undergo study assessments every 6-months. Patients eligible to continue with lenalidomide maintenance therapy will continue with the last tolerated dose of lenalidomide that was documented upon completion of BMT CTN 0702 maintenance therapy.

[figure not shown]
**Accrual Objective:** It is anticipated that approximately 450 patients will be enrolled on this protocol based on assumed estimates of PFS from the BMT CTN 0702 study. The total sample size may be as low as 417 if the observed 3-year PFS on the BMT CTN 0702 is 55% but may be as high as 569 if the 3-year PFS is 75%.

**Study Duration:** Patients will be followed until death, progression, withdrawal from the study, or through the end of 2018.

**Interim Analysis:** No formal interim analyses are planned.

Figure 1: Study Schema

### 1. BACKGROUND AND RATIONALE

#### 1.1. Background

Therapeutic advances in multiple myeloma (MM) have resulted in substantially improved survival. Similarly, in a large population-based study of 45,595 MM patients, myeloma-specific 5-year median overall survival (OS) improved from 36% to 68% under age 50, and from 34% to 58% among patients of ages 51-65 years between 1973 and 2009.

Post-transplant consolidation and maintenance strategies have also yielded improved progression-free survival (PFS) and OS. The BMT CTN 0702 study randomized patients to receive two autologous hematopoietic cell transplants (HCT), or one autologous HCT and post transplant consolidation, or one autologous HCT with maintenance. Of note, all patients receive a total of 3 years of maintenance therapy using lenalidomide. Since the implementation of BMT CTN 0702, the experience with maintenance has broadened, and at least two large phase III clinical trials that continued lenalidomide maintenance for longer periods were associated with longer survival, compared to placebo. This long-term follow-up protocol focuses on extending the follow-up period for all patients on BMT CTN 0702 to assess long-term outcomes such as PFS and incidence of SPMs. A secondary objective is to provide patients with lenalidomide maintenance therapy free of charge until there is evidence of disease progression.

#### 1.2. Lenalidomide Maintenance in Multiple Myeloma

There are three phase III studies that examined lenalidomide maintenance therapy versus placebo following autologous hematopoietic stem cell transplant (AHSCT) (Table 1.2). The CALGB/ECOG 100104 (BMT CTN 0704) study randomized MM patients after induction therapy and single AHSCT to lenalidomide versus placebo until progression. The induction regimens varied, with 74% of patients receiving a thalidomide- or lenalidomide-based induction regimen. The median time to progression (TTP) was 46 months for the lenalidomide group and 27 months for the placebo group ( $P<0.001$ ). The 3-year PFS was 66% for the lenalidomide group and 39% for the placebo group ( $P<0.001$ ). At a median follow-up of 34 months, the 3 year OS rates were 88% for the lenalidomide group and 80% for the placebo group ( $P=0.028$ ). The study was updated in 2013 and with a median follow-up of 48 months, the OS was 80% for the lenalidomide group and 70% for the placebo group ( $P=0.008$ ). The study was un-blinded at a median follow-up of 26 months because the primary endpoint (TTP) had been met and 67% of eligible placebo patients crossed over to receive lenalidomide. A TTP and OS benefit for the lenalidomide arm remains despite the cross-over.

The IFM 05-02 study treated MM patients after induction with a single (79%) or tandem AHSCT (21%) followed by a 2 cycle consolidation with lenalidomide before randomization to lenalidomide maintenance, originally until progression. The induction regimens were vincristine, doxorubicin and dexamethasone (VAD) or bortezomib and dexamethasone (VD). Approximately 25% of patients received consolidation with dexamethasone, cyclophosphamide,

etoposide and cisplatin before AHSCT. The median PFS was 41 months for the lenalidomide group and 23 months for the placebo group respectively ( $P<0.001$ ). The 4 year PFS was 43% for the lenalidomide group and 22% for the placebo group ( $P<0.001$ ). At 45 months of median follow-up, the OS was 74% for the lenalidomide group and 76% for the placebo group. The 4 year OS rate was 73% for the lenalidomide group and 75% for the placebo group respectively ( $P=0.7$ ). The study was un-blinded at median follow-up of approximately 30 months and all maintenance was stopped at a median time of 32 months for the lenalidomide arm due to concern regarding second primary malignancy (SPM) development (Section 1.3). At a median follow-up of 60 months from randomization, lenalidomide maintenance improved PFS (42%) when compared to placebo (18%) ( $P<0.0001$ ). The 5 year OS is 68% in the lenalidomide group and 67% in the placebo group ( $HR=1$ ) and the median survival after first progression is 29 months for the lenalidomide group and 48 months in the placebo group ( $P<0.0001$ ).

**Table 1.2: Lenalidomide Maintenance after Autologous Hematopoietic Cell Transplantation for Multiple Myeloma**

Study	Number of Patients	Initial Dose (mg)	Maintenance versus no Maintenance	
			EFS or PFS	OS
McCarthy et al NEJM 2012	460	10	TTP 46 vs 27 months ( $P<0.001$ )	Median followup 34 m 85 vs 77% ( $P=0.028$ )
			3-year PFS rate 66% (95% CI, 59 to 73) vs 39% (95% CI, 33 to 48)	3 year OS rate 88 % (95% CI, 84 to 93) vs 80 % (95% CI, 74 to 86)
			EFS 43 vs 27 months ( $P<0.001$ )	
McCarthy et al Clin Lym Myelom Leuk 2013 (Update)				Median followup 48 m 80 vs 70% ( $P=0.008$ )
Attal et al NEJM 2012	614	10	PFS 41 vs 23 months ( $P<0.001$ )	Median followup 45 m 74 vs 76% ( $P=0.7$ )
			4 year PFS 43 vs 22% ( $P<0.001$ )	4 year OS 73 vs 75% (NS)
			EFS 40 vs 23 months ( $P<0.001$ )	
Attal et al ASH 2013 abstr 206			5 year PFS 42% vs 18% ( $P<0.001$ )	Median followup 70 m 5 year OS 68 vs 67% (NS)
Boccardo et al JCO 2013	202 (NIT) 200 (IT)	10 (3 of 4 weeks monthly)	Median PFS (combining NIT and IT groups) 37 vs 26 months ( $P<0.001$ )	5 year OS (combining NIT and IT groups) 75 versus 58% ( $P=0.02$ )

Study	Number of Patients	Initial Dose (mg)	Maintenance versus no Maintenance	
			EFS or PFS	OS
Palumbo et al ASH 2013 abstr 763	194 (NIT) 195 (IT)	10: days 1 to 21 of 28 days +/- P 50: every other day	3 year PFS (combining NIT and IT groups) RP: 60% vs 38% for R alone (P=0.003)	31 month median followup (combining NIT and IT groups) 3 year OS (NIT and IT) ND

EFS: Event-free survival includes deaths, progressions and second cancers; IT: Intensive Therapy; NIT: Non-intensive therapy; ND: No difference, NS: Not significant; OS: Overall Survival; P: Prednisone, PFS: Progression-Free Survival, R: Lenalidomide. Adapted with permission from McCarthy PL. Part I: the role of maintenance therapy in patients with multiple myeloma undergoing autologous hematopoietic stem cell transplantation. *J Natl Compr Canc Netw.* 2013 Jan 1;11(1):35-42.

Another lenalidomide maintenance study following chemotherapy versus tandem autologous HCT has been reported; RV-MM-PI-209. At a median follow-up of 49 months from chemotherapy versus tandem autologous HCT and a median follow-up of 35 months from randomization to lenalidomide maintenance versus no maintenance, the median PFS for lenalidomide maintenance was 37 months (including autologous HCT and non-HCT patients received maintenance) versus 26 months for patients not receiving maintenance (P<0.0001). The 5 year OS estimates were 75% and 58% for the lenalidomide maintenance and no maintenance groups respectively (P=0.02). A meta-analysis of IFM 05 02, CALGB 100104, RV-MM-PI-209 (MPR vs Mel200) and MM 015 (a non-transplant trial) found that lenalidomide maintenance when compared to placebo improves PFS and OS.

In another study by the GIMEMA (Gruppo Italiano Malattie EMatologiche dell'Adulto) Multiple Myeloma Working Group, newly diagnosed patients received lenalidomide and dexamethasone (RD) induction followed by randomization to cyclophosphamide/ lenalidomide/dexamethasone (CRD) or tandem autologous HCT with melphalan, and a second randomization occurred to lenalidomide/prednisone versus lenalidomide maintenance until progression. There was superior PFS for the lenalidomide/prednisone maintenance arm when compared to lenalidomide alone: 62% versus 38%, (p=0.003).

### 1.3.Second Primary Malignancies

The lenalidomide group in CALGB/ECOG 100104 (BMT CTN 0704) had an increased incidence of hematologic toxicities (primarily neutropenia) and an increase in second primary malignancies (SPM). There were 8/231(3.5%) hematologic malignancies, primarily Acute Myeloid Leukemia/Myelodysplastic Syndrome (AML/MDS) in lenalidomide group patients versus 1/229 (0.4%) in placebo group patients. There were 10/231 (4.3%) versus 5 (2.1%) solid tumors in lenalidomide group and placebo group patients respectively, and 4/231 (1.7%) versus 3/229 (1.3%) non-melanoma skin cancers. In the 2013 update, one AML was reported in the lenalidomide arm (total 9/231 hematologic malignancies) and one case of ALL and MDS in two placebo arm patients who crossed over to lenalidomide. One solid tumor (renal cell carcinoma) was reported in another cross over patient and 4 non-melanoma skin cancers were reported; 3 in

the lenalidomide arm and one in a cross over placebo patient. The cumulative incidence risk (CIR) for the development of SPM was greater for the lenalidomide group when compared to the placebo group ( $p < 0.008$ ). The CIR of progressive disease ( $p < 0.001$ ) or death ( $p < 0.002$ ) were greater for the placebo group when compared to the lenalidomide group. When including deaths, progressions and SPMs as events, the median EFS was 43 months for the lenalidomide group and 27 months for the placebo group ( $P < 0.001$ ).

The placebo group patients in the IFM 05-02 study did not cross over to receive lenalidomide at un-blinding. The lenalidomide group had an increased incidence of hematologic toxicities (primarily neutropenia) and an increase in SPMs. There were 13/306 (4.2%) hematologic malignancies, (primarily Acute Lymphoblastic Leukemia (ALL) and Hodgkin Lymphoma and AML/MDS) in lenalidomide group patients versus 5/302 (primarily AML/MDS only) in placebo group patients. There were 10/306 (3.3%) versus 4/302 (1.3%) solid tumors in the lenalidomide group and placebo group patients respectively and 5/306 (1.6%) versus 3/302 (1.0%) non-melanoma skin cancers. When including deaths, progressions and SPMs as events, the median EFS was 40 months for the lenalidomide group and 23 months for the placebo group ( $P < 0.001$ ). An updated analysis was recently presented.

The SPM rate was approximately 4.5% in both maintenance arms (AHSCT and non-AHSCT). The risk factors for SPM development are not fully defined. A meta-analysis was undertaken of 6383 NDMM patients treated on Phase III transplant and non-transplant clinical trials, 3218 receiving lenalidomide maintenance and 3165 receiving no maintenance. The CI of hematologic SPMs was higher for patients receiving lenalidomide maintenance when compared to placebo arm patients (HR: 3.8; 95% CI 2.11-6.86;  $p < 0.001$ ). The CI of death at 60 months was 26.2 (95% CI 22.4 -28.8) for the lenalidomide arm and 36.3 (95% CI 25.9-46.6) for the no maintenance arm. There was a higher incidence of hematologic SPMs with oral melphalan when compared to IV melphalan (HR 3.3; 95% CI 1.46-7.46  $p = 0.004$ ). Previous work has demonstrated that monoclonal gammopathy of unknown significance (MGUS) and MM have both been associated with the development of AML/MDS. It is uncertain as to what the bone marrow defect is in MGUS and MM patients (not having received anti-MM therapy) that predisposes them to AML/MDS development.

#### **1.4. Rationale for Study**

This current protocol has the objective to compare long-term outcomes based on the randomized treatment groups from the BMT CTN 0702 protocol. All consenting patients will continue to be monitored for the development of long-term complications with emphasis on second primary malignancies. Patients who do not consent to the long-term follow-up mechanism or who have experienced progression on the BMT CTN 0702 study will be followed through the standard CIBMTR long-term follow-up mechanism. Additionally, the protocol will extend the duration of lenalidomide maintenance for all patients enrolled in the BMT CTN 0702 study who have completed 3 years of maintenance and have not experienced disease progression.

## CHAPTER 2

### 2. STUDY DESIGN

#### 2.1. Study Overview

This study is designed to compare long-term outcomes among patients randomized on the BMT CTN 0702 protocol. All patients who consent will be followed for death, progression, SPMs and QOL. Patients who do not consent to the long-term follow-up mechanism or who have experienced progression on the BMT CTN 0702 study will be followed through the standard CIBMTR long-term follow-up mechanism. Additionally, patients who are eligible and are willing to continue with lenalidomide as maintenance therapy will be provided lenalidomide free of charge. These patients will continue to receive lenalidomide as maintenance therapy until disease progression or discontinuation due to toxicity, death, or withdrawal from the study. The endpoints assessed will include progression-free survival (PFS), overall survival (OS), event-free survival (EFS), incidence of second primary malignancies (SPM) and health quality of life (QOL).

#### 2.2. Hypothesis and Specific Objectives

##### 2.2.1. Hypothesis

Use of novel anti-myeloma agents will improve long-term PFS after high-dose melphalan followed by autologous hematopoietic cell transplantation (HCT) as compared to a second autologous transplantation.

##### 2.2.2. Study Objectives

The primary objective of this long-term follow-up protocol is to compare the PFS as a time to event analysis from randomization on the BMT CTN 0702 protocol between the three randomized treatment arms as a pairwise comparison. The analysis will be conducted once all alive patients have been followed for 5-years post randomization on the BMT CTN 0702 protocol.

##### 2.2.3. Secondary objectives include:

- Overall survival from randomization on the BMT CTN 0702 protocol;
- Event-free survival from randomization on the BMT CTN 0702 protocol;
- Incidence from randomization on the BMT CTN 0702 protocol of second primary malignancies in long-term use of lenalidomide as maintenance therapy.
- Health Quality of Life

### **2.3. Patient Eligibility**

Patients must meet specified eligibility criteria to be enrolled on the study. All questions regarding eligibility criteria should be directed to the BMT CTN 0702 Long-Term Follow-Up Protocol Coordinator at [contact].

#### **2.3.1. Initial Patient Eligibility Criteria for Long-Term Follow-Up Only**

Patients fulfilling the following criteria will be eligible to provide continued long-term follow-up data as part of this study:

1. Enrolled and randomized on the BMT CTN 0702 protocol
2. Alive at the completion of BMT CTN 0702 protocol specified follow-up defined as 4 years post-randomization
3. Patients without evidence of disease progression at the completion of BMT CTN 0702 protocol specified follow up. (see Section 3.1 for disease progression definition)
4. Signed Informed Consent Form
5. Patients with the ability to speak English or Spanish are eligible to participate in the HQL component of this trial.

#### **2.3.2. Patient Eligibility Criteria for Optional Long-term Lenalidomide Maintenance Therapy**

Patients fulfilling the following criteria will be eligible to provide continued long-term follow-up data AND receive long-term lenalidomide maintenance therapy as part of this study:

1. Enrolled and randomized to BMT CTN 0702
2. Completion of 3 years of maintenance therapy on BMT CTN 0702
3. Registered in the mandatory Revlimid REMS® program (formerly the RevAssist® for Study Participants (RASP) program), and be willing and able to comply with the requirements of the Revlimid REMS® program, including counseling, pregnancy testing, and phone surveys.
4. Signed informed consent form.
5. Patients with the ability to speak English or Spanish are eligible to participate in the HQL component of this trial.

#### **2.3.3. Patient Exclusion Criteria for Long-term Lenalidomide Maintenance Therapy**

Patients who meet any of the following criteria will be ineligible to receive long-term lenalidomide maintenance therapy as part of this study\*:

1. Patients who have evidence of disease progression prior to enrollment (see Section 3.1 for disease progression definition).

---

\* All patients will be followed for long-term outcomes.

2. Patients who were discontinued from BMT CTN 0702 lenalidomide maintenance therapy, for any reason, prior to the completion of the 3 years of 0702 maintenance.
3. Female patients who are pregnant (positive -BetaHCG) or breastfeeding.
4. Females of childbearing potential (FCBP) or men who have sexual contact with FCBP unwilling to use contraceptive techniques (Appendix B) during the length of lenalidomide maintenance therapy.
5. Patients who experienced thromboembolic events while on full anticoagulation during prior therapy with lenalidomide.
6. Patients unwilling to take DVT prophylaxis.
7. Patients who developed a second primary malignancy, excluding non-melanoma skin cancers after initiation of lenalidomide maintenance therapy on BMT CTN 0702.

## 2.4. Study Treatments

### 2.4.1. Lenalidomide

Lenalidomide will be administered initially at the patient's last documented dose prior to discontinuation of BMT CTN 0702 lenalidomide maintenance therapy. Cycle duration is 28 days. Patients will continue lenalidomide until disease progression, or discontinuation due to toxicity, death, or withdrawal from the study. Patients who discontinue lenalidomide due to any reason other than death, or withdrawal of consent will continue to be followed per Section 4.4.1

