**Table 2.4.2a – Suggested Treatment Modification Guidelines for Long-Term Lenalidomide**

Grade by NCI CTCAE# 	Action
Non-blistering rash Grade 2-3 (Generalized rash ≥ 25% BSA)	Hold lenalidomide: Follow weekly. If the toxicity resolves to ≤ grade 1 restart lenalidomide at next lower dose level.
Non-blistering rash Grade 4	Discontinue lenalidomide.
Desquamating (blistering) rash any Grade	Discontinue lenalidomide.
Erythema multiforme ≥ Grade 3 (Severe (e.g., generalized rash or painful stomatitis); IV fluids, tube feedings, or TPN indicated)	Discontinue lenalidomide. If toxicity resolves to < grade 1 restart at next lower dose level.

Grade by NCI CTCAE# 	Action
Sinus bradycardia/ other cardiac arrhythmia Grade 2 (Non urgent, medical intervention indicated OR Moderate)	Hold lenalidomide. If the toxicity resolves to $\leq$ grade 1 restart lenalidomide at next lower dose level .
<math>\geq</math> Grade 3 (Incompletely controlled or controlled with device- e.g. pacemaker or Severe)	Discontinue lenalidomide. If toxicity resolves to $<$ grade 1 restart at next lower dose level.
Allergic reaction or hypersensitivity Grade 2-3 (flushing; urticaria; dyspnea; drug fever $\geq$ 38°C – symptomatic bronchospasm; parenteral meds indicated)	Hold lenalidomide If the toxicity resolves to $\leq$ grade 1 restart lenalidomide at next lower dose level.
Grade 4 (anaphylaxis)	Discontinue lenalidomide
Venous thrombosis/embolism <math>\geq</math> Grade 3 (DVT or cardiac thrombosis; intervention indicated)	Hold (interrupt) lenalidomide and start anticoagulation. Restart therapy per institutional guidelines.
Glomerular filtration rate (Creatinine Clearance) <math>\geq</math> Grade 3 ( $\leq$ 25%LLN, chronic dialysis not indicated)	Hold (interrupt) lenalidomide. If creatinine clearance has improved to $\leq$ grade 2 restart at next lower dose level.
Other non-hematologic toxicity assessed as Lenalidomide-related <math>\geq</math> Grade 3	Hold (interrupt) lenalidomide. If the toxicity resolves to $\leq$ grade 2 restart lenalidomide at next lower dose level.
Hyperthyroidism or Hypothyroidism	Hold lenalidomide. Evaluate etiology, and initiate appropriate therapy. Restart lenalidomide at next lower dose level.

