**Table 2.4.2b – Lenalidomide Dose Reduction Steps During Long-Term Maintenance Therapy**

Lenalidomide Dose Reduction Steps for Non-Hematologic Toxicity	
Dose at Time of Toxicity	Dose reduction
15 mg daily	10 mg daily
10 mg daily	5 mg daily
5 mg daily	5 mg daily for 21 days every 28 days
5 mg daily for 21 days every 28 days	Discontinue lenalidomide

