**Table 2.4.2c – Lenalidomide Dose Modifications for Hematologic Toxicities**

Lenalidomide Dose Modifications for Hematologic Toxicities	
Dose at Time of Toxicity	Action
15 mg per day	If ANC is < 1000/ $\mu$ L or the platelet count is < 50,000/ $\mu$ L, then lenalidomide will be held for up to 8 weeks. Lenalidomide drug may be re-instituted at 10 mg per day once the ANC is $\geq$ 1000/ $\mu$ L and the platelet count is $\geq$ 50,000/ $\mu$ L. If, however, after an 8 week treatment delay, the ANC remains < 1000/ $\mu$ L or the platelet count < 50,000/ $\mu$ L, maintenance therapy will be discontinued.
10 mg per day	If ANC is < 1000/ $\mu$ L or the platelet count is < 50,000/ $\mu$ L, then lenalidomide will be held for up to 8 weeks. Lenalidomide may be re-instituted at 5 mg per day once the ANC is $\geq$ 1000/ $\mu$ L and the platelet count is $\geq$ 50,000/ $\mu$ L. If however, after an 8 week treatment delay, the ANC remains < 1000/ $\mu$ L or the platelet count < 50,000/ $\mu$ L, maintenance therapy will be discontinued.
5 mg per day	If ANC is < 1000/ $\mu$ L or the platelet count is < 50,000/ $\mu$ L, then lenalidomide will be held for up to 8 weeks. Once the ANC is $\geq$ 1000/ $\mu$ L and the platelet count is $\geq$ 50,000/ $\mu$ L, then lenalidomide may be re-instituted at 5 mg per day for 21 days of a 28-day cycle. If, however, after an 8 week treatment delay, the ANC remains < 1000/ $\mu$ L or the platelet count < 50,000/ $\mu$ L, maintenance therapy will be discontinued.
5 mg per day for 21 of 28 days	If ANC is < 1000/ $\mu$ L or the platelet count is < 50,000/ $\mu$ L, then maintenance therapy will be discontinued.

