**2.4.3. Lenalidomide Maintenance Dose Re-escalation:**

If a dose reduction has occurred and ANC  $\geq$  1000/ $\mu$ L and platelet count is  $\geq$  75,000/ $\mu$ L, the study drug dose may be re-escalated as shown in Table 2.4.2b, one step per cycle to a maximum of 15 mg daily.

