1.2.2 Accrual Plan and Randomization

Participants were eligible to accrue on to BMT CTN 07LT as soon as they finished the earlier of 3 years of maintenance therapy on BMT CTN 0702 or four years of follow up on BMT CTN 0702. The protocol was approved after some participants had already finished 3 years of maintenance on BMT CTN 0702 so they were eligible to enroll when the protocol was activated, and there may have been a period when the participant was on commercially-available lenalidomide or other treatment. The protocol was activated in March 2015, and accrual was targeted through the beginning of 2018 to allow a window of time after the last person enrolled on BMT CTN 0702 would be eligible for BMT CTN 07LT.

Randomization occurred on the parent BMT CTN 0702 trial, which had a 1:1:1 randomization ratio with permuted blocks. Randomization on the parent trial was also stratified by patient risk and center. There was no additional randomization on BMT CTN 07LT.

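### The first 07LT lenalidomide dose is fixed at the last 0702 dose, so a participant whose dose was lowered for toxicity between the two studies would start above the dose last tolerated

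*Protocol*

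**What the plan says.** Protocol 2.4.1 gives the starting rule: "Lenalidomide will be administered initially at the patient's last documented dose prior to discontinuation of BMT CTN 0702 lenalidomide maintenance therapy". SAP 1.4 carries the same sentence. The synopsis (Treatment/Follow-Up) speaks of a tolerated dose, but takes it as documented when 0702 maintenance was completed. None of the three makes an exception for a later dose change.

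SAP 1.2.2 explains that 07LT was approved after some participants had already finished three years of 0702 maintenance. For them, "there may have been a period when the participant was on commercially-available lenalidomide or other treatment". The protocol was activated in March 2015.

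Protocol 2.4.3 governs increases once study drug has been reduced. With ANC at least 1000/µL and platelets at least 75,000/µL, "the study drug dose may be re-escalated as shown in Table 2.4.2b, one step per cycle to a maximum of 15 mg daily". Table 2.4.2b lists the levels: 15 mg daily, 10 mg daily, 5 mg daily, and "5 mg daily for 21 days every 28 days", after which drug is stopped.

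**The concern.** The starting rule looks back to the end of 0702 maintenance. For a participant who went straight from 0702 to 07LT, that is the current dose and the rule is sound. For a participant with an interval on commercial drug, it may be out of date. If toxicity in that interval led to a lower dose, the rule prescribes a return to the earlier, higher one at the first 07LT cycle.

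What is at stake is the safety of individual participants. The synopsis shows that tolerance was the intended basis for the dose. A prescriber would probably start lower, but that prescriber would be departing from 2.4.1. The protocol should itself prescribe the safer action.

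**Working it through.** The plan gives no figure to reproduce. The check sets the rules side by side for one assumed participant who completes 0702 maintenance on 10 mg daily, is lowered to 5 mg daily for toxicity on commercial lenalidomide, recovers, and enrols on 07LT.

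1. **Starting dose (Protocol 2.4.1, SAP 1.4).** The last documented 0702 dose is 10 mg daily, so the first 07LT dose is 10 mg daily. The commercial dose does not enter the rule.
2. **Synopsis.** The reference time is completion of 0702 maintenance, so the answer is again 10 mg daily.
3. **The same history on study drug (2.4.3).** After a reduction to 5 mg daily, a return to 10 mg daily is optional, needs both count conditions, and is limited to one step per cycle. At 28 days per cycle, one step up comes no earlier than day 1 × 28 = 28.
4. **Toxicity rules (2.4.2, Table 2.4.2a).** These act while a lenalidomide-related toxicity is present. A toxicity that settled on the lower commercial dose triggers nothing at entry.
5. **Assessments at entry (4.4.2).** A history and physical is done at initiation and a CBC before each monthly supply. Neither is linked to a starting-dose rule.
6. **Exclusions (2.3.3).** Item 5 (thromboembolism on full anticoagulation during earlier lenalidomide) and item 7 (second primary malignancy after 0702 lenalidomide began) both reach into the gap. Neither covers a participant who was simply reduced for another toxicity.

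So nothing in the text examined moves this participant off 10 mg daily.

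**Two checks on the remedy.**

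- *Off-ladder doses.* Milligrams per 28-day cycle on Table 2.4.2b are 15 × 28 = 420, 10 × 28 = 280, 5 × 28 = 140 and 5 × 21 = 105. A commercial schedule need not match any of these. Protocol Table 1.2 shows 10 mg for three of four weeks in use elsewhere, which is 10 × 21 = 210 mg, between the 280 and 140 levels. Protocol 2.7.1 describes supply in 5 mg capsules only. A starting rule that takes in commercial doses therefore needs a rounding instruction; here 210 rounds down to 140 (5 mg daily).
- *Return to the earlier dose.* Section 2.4.3 applies only after a dose reduction. A participant started low because of a reduction on commercial drug might not meet that condition, so the remedy must say that such a reduction counts. The 0702 dose is then reachable after one, two or three steps no earlier than day 28, 56 or 84 (1, 2 or 3 × 28).

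**The case against.** The strongest reply is that the harm needs a chain of events that no document shows to have occurred: 0702 maintenance finished before activation, commercial lenalidomide, a reduction, optional re-entry, and a prescriber who disregards the lower dose. SAP 1.2.2 says only that such an interval may have existed and mentions no reduction. The higher dose is also one already taken on 0702. This limits the size of the point and is accepted. It does not make the rule right for a participant who was reduced. The toxicity guidelines in 2.4.2 are labelled as suggestions, but that latitude is not attached to 2.4.1.

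Four stronger readings are tempting, and the documents do not support them.

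- **That 2.4.1 contradicts or overrides 2.4.3.** Section 2.4.3 concerns re-escalation of study drug. A first 07LT dose is not a re-escalation, and a cut on commercial drug is not a study-drug reduction. The stepwise increase is avoided in effect only.
- **That platelets of 50,000 to 74,999/µL expose a defect.** Table 2.4.2c holds drug for low ANC "or the platelet count is < 50,000"/µL, and so accepts dosing at every level, 15 mg included, from 50,000 upward. A stricter limit for a voluntary increase is an ordinary asymmetry.
- **That ratios between ladder levels measure the harm.** One can compute 140/105 = 1.33 up to 420/105 = 4.00, but these describe the spacing of the table. How many participants were reduced, and by how much, is not reported.
- **That a new exclusion is needed.** Exclusion 2 covers stopping "for any reason, prior to the completion of the 3 years of 0702 maintenance" and so does not name a later permanent-stop toxicity such as the row "Desquamating (blistering) rash any Grade". That is a separate eligibility matter, and it supposes that drug would be re-prescribed after such an event. Even the stop rows differ, since some read "Discontinue lenalidomide. If toxicity resolves to < grade 1 restart at next lower dose level". It cannot be settled without the 0702 protocol and the Appendix D information sheet, which were not available.

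**Conclusion.** The concern holds in a narrow form. For a participant whose lenalidomide was lowered for toxicity between 0702 maintenance and 07LT, Protocol 2.4.1 as written prescribes a first dose above the one most recently tolerated. This is a rule that gives the wrong answer in an identifiable case, and that the rule extends to this case follows from the absence of any exception.

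The size is low. The number affected is unknown and may be small. The entry assessments, the rules for toxicity still present, and exclusions 5 and 7 give partial protection. The primary PFS comparison is unaffected: it runs by 0702 randomized arm from 0702 randomization, and the starting dose is not an input to it. The conclusion assumes that at least one participant had a gap reduction and that no exception appears in the 0702 protocol or Appendix D. It is worth considering because the correction is nearly free.

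**What to change.** In Protocol 2.4.1 and the synopsis, mirrored in SAP 1.4 for consistency, state:

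> The 07LT starting dose is the lower of the last documented 0702 maintenance dose and the most recent tolerated lenalidomide dose from any source before 07LT enrollment, rounded down to the nearest Table 2.4.2b level. A reduction made between 0702 and 07LT counts as a dose reduction for Section 2.4.3, and any later increase follows that section.

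Doses on different schedules can be compared by total milligrams per 28-day cycle. No exclusion, hold threshold or analysis changes, and participants whose dose never changed are untouched. The clinical cost is a possibly lower dose for a few cycles in a small number of participants. The change protects only those who start drug after it is made; SAP 1.2.2 targeted accrual through the beginning of 2018. The protocol edit does the protective work, since SAP 1.4 only describes treatment.
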